#### Other daily characteristics

Daily variables will be reported according to the description in **Table 6**. Absolute differences between groups will be calculated using median regression for continuous variables (reported as median difference) and generalized linear models with binomial distribution and an identity link for binary variables (reported as difference in percentages). Plots comparing daily variables among the groups will be constructed (presenting the data as mean and 95% confidence interval in each time point).

#### Primary outcome

The effect of 'individualized high PEEP' compared to low PEEP of the incidence of PPC will be assessed using a mixed-effect generalized linear model with binomial distribution and identity link, with sites included as random effects to

account for the clustering effect and reported as absolute difference with a twosided 95% confidence interval. Results will be presented in a table of outcomes (**Table 7**). To support interpretation, a confidence distribution for the primary outcome using a normal approximation on the estimated absolute difference will be calculated. The confidence distribution will be computed to provide the frequentist probability that the absolute difference is less than 0. In addition, the confidence distribution will be reported in a plot.

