#### Randomization and blinding

Eligible patients are randomly allocated in a 1:1 ratio to the 'individualized high PEEP' or 'low PEEP' strategy. The allocation sequence is computer–generated by an independent investigator using permuted blocks of different block sizes, with a maximum block size of eight and stratified per center and BMI ( $\leq$  30 vs. > 30 kg/m^2). Randomization is performed by local investigators patient–by–patient employing a dedicated, password protected, SSL–encrypted website.

At each site, at least two investigators are involved with the study. One investigator randomizes the patients immediately before surgery and is responsible for the trial intervention and data collection. A second investigator remains blinded for the randomization and is responsible for postoperative data

collection. The surgeon and patient are kept blind to the allocated ventilation strategy. Since PEEP can be adjusted at any time point upon the surgeons' request or because of concerns about patient's safety, and since patients do not profit from knowing to which group they are allocated to, unblinding is not applicable.

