#### Statistical analyses

All statistical analyses will be conducted on an intention-to-treat basis, with patients analysed according to their assigned treatment arms, except for cases lost to follow up or withdrawal of informed consent. In addition, a per-protocol analysis will be conducted. Variables will be expressed as counts and percentages, means and standard deviations (SD), or medians and interquartile ranges (IQR) whenever appropriate.

The primary and secondary outcomes will be assessed using a two–sided superiority hypothesis test with a significance level of 0.05 and presented with a two–sided 95% confidence interval. In addition to the unadjusted *p* values for secondary outcomes, a Holm–Bonferroni procedure will be applied to control for multiple testing. Analyses will be performed using the software R (R Core Team, 2016, Vienna, Austria). A list of proposed tables and figures is in **Table 2**.

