#### Secondary outcomes

For binary outcomes, the effect of 'individualized high PEEP' compared to 'low PEEP' on the incidence of PPC will be assessed using a mixed–effect generalized linear model with binomial distribution and identity link, with sites included as random effects to account for the clustering effect and reported as absolute difference with a two–sided 95% confidence interval. For continuous outcomes, the comparison will be made using a mixed-effect median regression with sites also including as clustering effect, and reported as median difference with a two–sided 95% confidence interval as median difference with a two–sided 95% confidence as median difference with a two–sided 95% confidence interval. In addition, a Holm–Bonferroni correction to control the family–wide error rate to the *p* values for all 17 secondary outcomes will be done and presented in a Table.

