#### Subgroup analysis

Treatment effects on incidence of PPC will be analyzed according to the following predefined subgroups: 1) age < 65 years  $vs \ge 65$  years; 2) body mass index < 30 kg/m^2 vs BMI  $\ge$  30 kg/m^2; 3) baseline SpO2 < 96% vs SpO2  $\ge$  96%; 4) moderate vs high risk for PPC according to the ARISCAT risk score (< 45 vs.  $\ge$  45); 5) duration of surgery < 3 hours  $vs \ge$  3 hours; and 6) planned destination to ICU or HDU vs ward. Analyses of heterogeneity of effects across subgroups will be performed with the use of treatment–by–subgroup term added to the primary model and will be presented in a forest plot.

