# Table 2 – List of proposed tables and figures

|               | Description   |
|---------------|---|
| Main paper    |   |
| Table 1       | Baseline Characteristics of the Included Patients   |
| Table 2       | Ventilation and Intraoperative Characteristics  |
| Table 3       | Primary and Secondary Outcomes  |
| Figure 1      | Participant Flow Diagram  |
| Figure 2      | Postoperative Pulmonary Complications in Prespecified Subgroups
A forest plot showing the absolute difference and two-sided 95% confidence intervals with p value for interaction calculated via a test for treatment-by-subgroup interaction in
the regression model. A solid line of reference in the number 1 and a dashed line of reference in the overall effect will be shown.  |
| Online Supple | ement   |
| eTable 1      | Rate of Missing Data A table showing the rate of missing data.  |
| eTable 2      | Additional Intraoperative Characteristics
A table showing additional intraoperative characteristics.   |
| eTable 3      | Rescue Therapies in Included Patients
A table showing the steps of rescue therapies in patients receiving rescue in each arm.  |
| eTable 4      | Protocol Deviations
A table reporting the protocol deviations in each arm.   |
| eTable 5      | Daily Assessment of Included Patients
A table showing characteristics over the first 5 days of follow-up.  |
| eTable 6      | Multiplicity adjustment for secondary outcome analyses
A table showing the observed p values for all the secondary outcomes and ordered from the lower until the higher and the corrected p values using a Holm–Bonferroni correction  |
| eTable 7      | Sensitivity Analyses for the Primary Outcome
A table showing the proposed sensitivity analyses for the primary outcome (count analysis, common effect test, average relative effect test and heterogeneity of treatment effect)  |

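### The primary and binary secondary models leave out BMI stratum and ARISCAT at a small cost in precision, and no alternative is given if the identity-link mixed model cannot be fitted

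*SAP*

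**What the plan says.** - **SAP, Primary outcome.** The model is a "mixed-effect generalized linear model with binomial distribution and identity link, with sites included as random effects to" allow for clustering, reported as an absolute difference with a 95% confidence interval. Treatment and site are its only terms.
- **SAP, Secondary outcomes.** Binary outcomes use the same "generalized linear model with binomial distribution and identity link, with sites included as random effects to account for the clustering effect". A Holm–Bonferroni correction of the p "values for all 17 secondary outcomes will be done and presented in a Table" follows.
- **SAP, Randomization and blinding.** Allocation uses permuted blocks "with a maximum block size of eight and stratified per center and BMI", cut at 30 kg/m². ARISCAT is not a stratification factor.
- **SAP, Subgroup analysis and Table 3.** ARISCAT is a baseline variable and defines the subgroup "moderate vs high risk for PPC according to the ARISCAT risk score". It enters no main model.
- **SAP, Statistical analyses.** "Analyses will be performed using the software R"; no package or estimator is named.
- **SAP, Modifications from the original analysis plan.** This model replaced a risk ratio with a chi-square test. Neither here nor elsewhere does the SAP say what happens if the model does not converge or gives fitted probabilities outside 0 to 1.

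**The concern.** A factor used to stratify randomisation, and a risk score collected at baseline for this very outcome, normally go into the primary model because they buy precision at almost no cost. Here both are left out.

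The second issue is more practical. An identity-link binomial model with a normal random site effect adds a symmetric site deviation to a probability. When the probability is near zero, or some sites have no events, the linear predictor goes below zero and the fit stops. Of the secondary rows of Table 7, 15 are binary by nature, among them septic shock, anastomotic leakage, new arrhythmias and hospital mortality. If the model fails, someone must choose another after the data are in. That choice then supplies the reported difference, its interval and a p value whose rank affects the Holm–Bonferroni adjustment of the others. The SAP's Introduction says the plan exists to prevent data-driven analysis.

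**Working it through.** **1. Sample size as stated.** Inputs from SAP, Sample size: 34% vs 27.2%, type I error 5% (two-sided, from Statistical analyses), power 80%, dropout 2%, 1:1.

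- Unpooled: n = (1.96 + 0.8416)² × (0.2244 + 0.1980) / 0.068² = 717.0 per arm; 2 × 717.0 / 0.98 = 1,463.
- Pooled variance: 719.8 per arm; 2 × 719.8 / 0.98 = 1,469.

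The stated 1,468 is reproduced without any covariate.

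**2. Precision without covariates.** With 1,468 × 0.98 ≈ 1,438 analysed, 719 per arm, SE = √[(0.2244 + 0.1980)/719] = 2.42 points. The 95% half-width is 1.96 × 2.42 = 4.75 points.

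**3. Gain from ARISCAT.** The SAP gives no c-statistic, so 0.55 to 0.70 is assumed. For a binormal score with separation d = √2·Φ⁻¹(c), R² = Var(risk given score)/(0.306 × 0.694). Then power = Φ(2.8016/√(1−R²) − 1.96), half-width = 4.75·√(1−R²) and equivalent extra patients = 1,438·(1/(1−R²) − 1).

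| c | R² | Power | Half-width | Extra patients |
|---|---|---|---|---|
| 0.55 | 0.007 | 80.3% | 4.73 | 10 |
| 0.60 | 0.027 | 81.1% | 4.69 | 40 |
| 0.65 | 0.061 | 82.4% | 4.60 | 93 |
| 0.70 | 0.108 | 84.3% | 4.49 | 174 |

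**4. Gain from BMI alone.** Assumed: 15% to 35% of patients in the upper stratum, risk difference 5 to 15 points. R² = prevalence × (1 − prevalence) × difference²/0.2124 = 0.0015 to 0.024, giving power 80.1% to 80.9%.

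**5. Cross-checks by simulation.** A linear risk-difference model with both covariates (2,000 runs per setting; high ARISCAT in 30% with a 10 to 25 point difference, high BMI in 20% with 0 to 10 points) had a standard error 0.996 to 0.965 times the unadjusted one, and about 1 to 3 points more power. In 1,000 simulated trials with 20 sites, the stated model against the standardised logistic model gave 79.1% vs 79.8% at c = 0.55, and 80.3% vs 81.8% at c = 0.65.

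**6. Does the stated model fit?** Simulated trials of about 1,438 patients, lme4, between-site SD 0.3 on the logit scale unless noted. Package, site number and size, SD and secondary event rates are all assumptions.

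*Rare outcomes, failed fits:*

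| Incidence | 15 sites | 30 sites |
|---|---|---|
| 3% | 39 of 60 | 60 of 60 |
| 1% | 58 of 60 | 59 of 60 |
| 0.5% | 60 of 60 | 60 of 60 |

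Four starting values were tried per data set. A separate batch with two starting values gave errors in 31 of 40 (15 sites) and 39 of 40 (30 sites) at 3%, and 40 of 40 in both at 1%. The reason is visible by hand: at 1% with 30 equal sites of about 48 patients, 30 × 0.99^47.9 ≈ 19 sites are expected to have no event. With 10 sites the picture is milder: at 5%, 30 of 40 clean fits with equal sites and 11 of 40 with unequal sites; at 2%, 12 and 1 of 40; at 1%, none.

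*Primary outcome (34% vs 27.2%):*

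- 10 sites: 38 to 40 of 40 clean.
- 20 equal sites: 35 to 40 of 40 clean across batches, the rest warnings.
- 20 unequal sites: 28 to 33 of 40 clean.
- 30 unequal sites: error or warning in 70 of 120 (site SD 0, 0.3 and 0.6 pooled), 25 of 40, 21 of 40, 21 of 30 and 14 of 30; more than half in four of five batches.

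**7. Does the replacement fit?** The logistic mixed model with BMI and ARISCAT failed in 0 of 250 data sets in every rare-outcome setting. Type I error of its standardised difference (15 / 30 sites) was 4.4% / 5.6% at 3%, 6.8% / 2.0% at 1% and 0.4% / 3.0% at 0.5%. The simulation margin is about 1.96·√(0.05 × 0.95/250) = 2.7 points.

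**The case against.** **The covariates are optional.** The stratification and the model do not contradict each other, ARISCAT was never a stratification factor, and the gain rests on assumed c-statistics. This stands in part. A reader might infer that leaving out a stratification factor makes the test invalid or the trial underpowered. It does neither: the planned number is reproduced without adjustment. What is left is a small, nearly free gain.

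**The fitting failures belong to one package and to assumed rates.** Also fair. The SAP says only R, gives no secondary event rates and does not describe the sites. Penalised quasi-likelihood (glmmPQL in R's MASS package) returned estimates in 224 of 225 data sets, so the model is not impossible to fit in every software. That is no rescue, since its type I error was 15.5% at 1% incidence (200 runs, one setting). glmmTMB failed in every attempt made. Which secondary outcomes will be rare is unknown. Table 7 has 18 secondary rows by count (15 binary, 3 continuous) against the 17 in the text, so one cannot say that every rare row enters the Holm family.

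**A late further change to the primary model is unattractive.** The model was already changed once, the SAP was updated in January 2025, and recruitment was due to end in 2024. This is a good reason to let the sponsor keep the primary model, but not to leave it without a fallback.

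**Conclusion.** The point holds in two parts of unequal weight.

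- **Covariates:** a missed gain of about 0.3 to 4 power points, nearly all from ARISCAT and dependent on how well it predicts PPC in this at-risk population.
- **No alternative to the identity-link mixed model:** the more important part. For outcomes of 1% to 3% and 15 to 30 sites, the Secondary outcomes section followed in lme4 will usually give no usable result.

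Two stronger readings should be resisted. One is that the primary analysis will fail; with few or equal sites it fits, and the SAP does not give the layout. The opposite, that the primary model is safe at its event rates, is not supported either, because 30 unequal sites often break it. The gap therefore certainly concerns rare binary secondary outcomes and possibly the primary analysis. It is worth correcting, but does not threaten the validity of the trial. Confidence is medium, because package, site layout, site SD and event rates are assumed.

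**What to change.** Make the change before database lock and before any comparison by arm. (The SAP states that unblinding does not apply, so lock is the usable milestone.)

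- **(a) Binary secondary outcomes.** Estimate the absolute difference from a logistic model with random site effect, BMI stratum as randomised (≤30 vs >30) and baseline ARISCAT, by marginal standardisation with a delta-method or bootstrap 95% interval. If an arm has no events, report counts with an exact test and a score interval. At 719 per arm, the chance that at least one arm is empty is 1 − (1 − (1−p)^719)²: 0.15% at 1% incidence and 5.4% at 0.5%.
- **(b) Primary outcome.** Use the same standardised estimate as the main analysis, with the identity-link model as sensitivity analysis. Or keep the stated model and name the standardised estimate as the fallback on any error or convergence warning, and otherwise as a sensitivity analysis. The confidence distribution can use whichever estimate and standard error apply.
- **(c) Subgroups.** Keep the interaction on the scale of the planned figure: "A forest plot showing the absolute difference and two-sided 95% confidence intervals with p value for interaction". If the stated model is kept and fits, the interaction "term added to the primary model and will be presented in a forest plot" already does this. Otherwise test a difference in standardised absolute differences, not a logit interaction. A constant 6.8-point reduction is an odds ratio of 0.67 at 25% control risk and 0.75 at 43%, and with that constant effect the logit test rejected in 9.6% of 1,000 trials against 5.8%. Omit the BMI stratum term from the BMI subgroup model, where it nearly duplicates the subgroup term.

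**Cost.** Wording in three SAP sections and somewhat more code; no new data. The drawbacks are a further change to a model already changed once (avoided for the main primary analysis if the stated model is kept), simple imputation of any missing ARISCAT score, and little gain if ARISCAT predicts PPC weakly.

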#### Secondary outcomes

For binary outcomes, the effect of 'individualized high PEEP' compared to 'low PEEP' on the incidence of PPC will be assessed using a mixed–effect generalized linear model with binomial distribution and identity link, with sites included as random effects to account for the clustering effect and reported as absolute difference with a two–sided 95% confidence interval. For continuous outcomes, the comparison will be made using a mixed-effect median regression with sites also including as clustering effect, and reported as median difference with a two–sided 95% confidence interval as median difference with a two–sided 95% confidence as median difference with a two–sided 95% confidence interval. In addition, a Holm–Bonferroni correction to control the family–wide error rate to the *p* values for all 17 secondary outcomes will be done and presented in a Table.

#### Per-protocol analysis

The analysis for the primary endpoint will be repeated in patients who received treatment according to their respective randomisation arm. This includes patients with pre-approved protocol deviations. However, patients with non-pre-approved protocol deviations and protocol violations will be excluded.

#### Subgroup analysis

Treatment effects on incidence of PPC will be analyzed according to the following predefined subgroups: 1) age < 65 years  $vs \ge 65$  years; 2) body mass index < 30 kg/m^2 vs BMI  $\ge$  30 kg/m^2; 3) baseline SpO2 < 96% vs SpO2  $\ge$  96%; 4) moderate vs high risk for PPC according to the ARISCAT risk score (< 45 vs.  $\ge$  45); 5) duration of surgery < 3 hours  $vs \ge$  3 hours; and 6) planned destination to ICU or HDU vs ward. Analyses of heterogeneity of effects across subgroups will be performed with the use of treatment–by–subgroup term added to the primary model and will be presented in a forest plot.

#### Other exploratory analyses

Since the primary outcome of the present study is a composite one, the choice of the statistical method is an important part of designing because various methods provide different power, depending on the situation. In addition to the standard analysis described above, the following analyses will be performed:

- Count analysis: the number of positive component events (i.e., 'count') across the composite will be assessed; the groups will be compared on the count using a Wilcoxon rank sum test, and the odds ratio with the 95% confidence interval will be assessed with a proportional odds logistic regression model;
- Individual component analysis: the effect of the intervention in each component will be analyzed estimating the risk ratio and confidence intervals with Wald's likelihood ratio approximation test using a Bonferroni correction for multiple comparisons; the 99.5% Bonferroni–corrected confidence intervals will be reported (1 0.05/10 = 0.995);

- Common effect test: a multivariate (i.e., multiple outcomes per subject) generalized estimating equations (GEE) model will be used to estimate a common effect odds ratio across the components;
- Average relative effect test: the average relative effect test will be assessed by averaging the component-specific treatment effect from the distinct effects model, and testing whether the average is equal to zero. In the GEE distinct effect model a distinct treatment effect is estimated for each component; and
- Heterogeneity of treatment effect: heterogeneity of treatment effect across components will be assessed by a treatment-by-component interaction test in the distinct effects GEE model.

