#### Adherence to study interventions and ventilatory variables

Surgical and perioperative characteristics will be reported (**Tables 4** and **5**). Ventilatory variables and vital signs will be reported after intubation, one hour, and in the last hour of surgery and compared between the two groups. Absolute differences between groups will be calculated using median regression for continuous variables (reported as median difference) and generalized linear models with binomial distribution and an identity link for binary variables (reported as difference in percentages). Plots comparing ventilatory variables and vital signs among the groups during the first three hours of surgery and in the last hour will be constructed (presenting the data as mean and 95% confidence interval in each time point).

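### The count analysis and the ventilatory, intraoperative and daily between-arm models leave out site, which stratifies randomisation and is in the primary model; the loss is small but avoidable

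*SAP*

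**What the plan says.** - SAP, Randomization and blinding: allocation is 1:1 in permuted blocks, "stratified per center and BMI".
- SAP, Primary outcome: the model is a "mixed-effect generalized linear model with binomial distribution and identity link, with sites included as random effects". Secondary outcomes uses the same model for binary outcomes and a mixed-effect median regression with site for continuous ones. Subgroup analysis adds the interaction to the primary model, so it also carries site.
- SAP, Other exploratory analyses: for the number of positive components, "the groups will be compared on the count using a Wilcoxon rank sum test", with an odds ratio from a proportional odds model. For the common effect test, a GEE "model will be used to estimate a common effect odds ratio across the components"; the only clustering stated there is several outcomes per subject. No analysis in this section mentions site.
- SAP, Adherence to study interventions and ventilatory variables: "Absolute differences between groups will be calculated using median regression for continuous variables", and an identity-link binomial model for binary ones, with no site term. Other daily characteristics repeats this.
- SAP, Table 2, eTable 7: "A table showing the proposed sensitivity analyses for the primary outcome", listing the count, common effect, average relative effect and heterogeneity analyses. The individual component analysis is not on that list.

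**The concern.** When arms are balanced within site by design, between-site differences in outcome cannot favour one arm except through small block imbalances. An analysis that ignores site still leaves that variation in its error term. The reference distribution is then too wide for the design, and the test rejects less often than its nominal level.

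A sensitivity analysis is most readable when it changes only what it is meant to change. Here the handling of the composite and the effect measure change on purpose. Dropping site is a further change, and the SAP gives no reason for it. A somewhat weaker count result could partly reflect that omission. Most components of the composite rest on chest imaging, so recorded rates may well vary by site.

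The second issue is consistency. Intraoperative fluid balance and unplanned ICU admission each fall under two sections with different models, and both sets of results are due in main-paper tables with an interval and a p value.

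**Working it through.** **The plan's own figure.** Inputs from Sample size: 34% vs 27.2%, two-sided 5%, power 80%, dropout 2%. With mean rate 0.306 and pooled variance under the null:

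n = [1.96·√(2·0.306·0.694) + 0.8416·√(0.34·0.66 + 0.272·0.728)]² / 0.068² ≈ (1.277 + 0.547)² / 0.004624 ≈ 720 per arm.

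720/0.98 = 734.7, so 735 per arm and 1,470 in total, against the stated 734 and 1,468. The planned size is reproduced to within 2 patients and this point does not touch it.

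**Analytic check of direction.** Let ρ be the share of outcome variance due to site. Under site-stratified allocation the unstratified statistic has SD of about √(1−ρ), so its actual size is 2·[1 − Φ(1.96/√(1−ρ))]. This gives 4.9% at ρ = 0.01, 4.4% at 0.05 and 3.9% at 0.10. With ρ = 0 there is no loss.

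**Simulation of the rank test.** The SAP gives neither the number of sites nor the between-site variance, so both are assumed.

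- Set-up A: about 1,440 patients, 30 sites, arms balanced within site. P(count ≥ 1, 2, 3, 4) = 34%, 17%, 8%, 3%, the last three assumed; shift equal to 34% vs 27.2%. Comparator: van Elteren test. 3,000 runs.
- Set-up B: 1,468 patients, 20 or 35 sites, blocks of 4, 6 or 8 within site and BMI stratum, ten-component count. Comparator: ranks centred within site. 2,000 runs. Its control rate came out at about 26 to 28%, not 34%, so its absolute power is lower; the contrast between tests is what matters.

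| Site SD (logit) | Set-up | Size, unstratified vs stratified | Power, unstratified vs stratified | Power loss (points) |
|---|---|---|---|---|
| 0.3 | A | 4.7% vs 5.1% | 81.7% vs 82.3% | 0.6 |
| 0.3 | B, 20 sites | 4.4% vs 4.9% | 74.6% vs 74.9% | 0.3 |
| 0.3 | B, 35 sites | 5.2% vs 5.4% | 73.3% vs 73.5% | 0.2 |
| 0.6 | A | 4.4% vs 5.1% | 82.3% vs 83.8% | 1.5 |
| 0.6 | B, 20 sites | 4.3% vs 5.1% | 72.8% vs 74.2% | 1.4 |
| 0.6 | B, 35 sites | 4.3% vs 4.8% | 73.0% vs 74.3% | 1.3 |
| 1.0 | A | 3.1% vs 4.3% | 83.6% vs 88.3% | 4.7 |
| 0.9 | B, 20 sites | 3.3% vs 4.1% | 72.5% vs 75.4% | 2.9 |
| 0.9 | B, 35 sites | 3.2% vs 4.6% | 71.9% vs 74.7% | 2.8 |

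Monte Carlo error is about 0.4 to 0.5 points for size and 0.7 to 1.0 for power. Both tests were run on the same simulated data, so their differences are steadier than that. With no site variation (set-up B), power was 74.6% for both tests at 20 sites, and 75.2% unstratified vs 74.6% stratified at 35, which is within simulation error.

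**Odds ratios behave differently.** In a binary logistic analogue (30 assumed sites, about 1,440 patients, 34% vs 27.2%, site as fixed effects, 200 runs), adding site raised the standard error of the log odds ratio by 2%, 5% and 10% at site SD 0.3, 0.6 and 1.0. The estimate also moves away from 1, so any gain lies in the test and not in a narrower interval.

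**Tables 4 and 7 side by side.** Fluid balance is a row of Table 4, governed by the plain median regression, and of Table 7, governed by the mixed model with site. Unplanned admission is likewise in both. The Table 4 row is labelled ICU/HDU and the Table 7 row ICU, so for that outcome the definition needs aligning as well.

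**The case against.** The strongest reply is that nothing depends on this. The section is headed as exploratory, no decision rule uses it, the error runs in the cautious direction, and the loss is close to simulation noise unless sites differ markedly. The SAP's stated reason for these analyses is that methods differ in power, not that they replicate the primary model like for like. For the proportional odds and GEE models the text is silent on site rather than excluding it. Rare components spread over many sites would leave empty strata and unstable site coefficients. BMI also stratifies randomisation, yet the primary model omits it too.

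Most of this stands, and it sets the rank of the point. It does not remove it. A Wilcoxon rank sum test as named cannot carry site, silence in the other models leaves the choice to the analyst, and the overlap between Tables 4 and 7 is independent of any assumed variance. BMI is a separate matter: the aim here is only to match the primary model.

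A reader might infer that all five composite analyses have intervals that are too wide and that adding site would narrow them. The documents do not support that. For odds ratios the interval widens. The heterogeneity test compares components within the same patients, so the between-site argument does not carry over directly. The component analysis is not among those eTable 7 labels as sensitivity analyses.

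**Conclusion.** A minor point that holds. The unstratified rank test is mildly conservative if, and only if, sites differ in recorded complication rates. The loss is negligible at a site SD of 0.3 (size about 4.4 to 5.2%, power loss under 1 point), about 1 to 1.5 points of power at 0.6, and about 3 to 5 points with size near 3% at 0.9 to 1.0. These figures rest on assumed numbers of sites, site variances and count distributions. The primary estimate, its p value and the sample size are unaffected.

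For the four analyses in eTable 7, leaving site out is an avoidable extra difference from the primary model, besides the intended changes in outcome handling and effect measure. The two treatments of fluid balance and unplanned ICU admission should be reconciled whatever the between-site variance is.

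**What to change.** - Other exploratory analyses: replace the Wilcoxon rank sum test with a site-stratified (van Elteren) test and add a site random intercept to the proportional odds model. State that this odds ratio is conditional on site and that the gain is in the test, not in a narrower interval.
- Adherence and Other daily characteristics: use the site term given under Secondary outcomes, at least for outcomes that also appear in Table 7. Alternatively, report each such outcome once. Align the ICU and ICU/HDU labels.
- Component risk ratios and GEE models: site adjustment is optional because rare components make it unstable. If site is left out, one sentence should say so and why.

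Cost: a few sentences of SAP text and a few lines of code, with no new data. Downsides: the odds ratio becomes site-conditional, and sites with patients in only one arm contribute nothing to the stratified test.
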